- Management with Extracorporeal membrane oxygenation (ECMO) and/or nitric oxide.
- Temperature less than 36.5 C or greater than 37.5 C.
- Patient under pharmacological sedation or use of beta-blockers.

- Congenital heart disease, operated on or not.
- Congenital malformations.
- Surgical emergencies or recovery from a surgical procedure performed within the last 48 hours.

Sample size

The sample size was determined using the G*Power 3.1.9.7 program, with a confidence level of 95%, statistical power of 90%, mean difference in heart rate between the live music therapy group (140 bpm), prerecorded music therapy group (127 bpm), and the control group (147 bpm). A total sample size of 45 was calculated, with a ratio of 1:1:1 between groups. This equates to 15 participants in each group.

Sample Selection

Stratified random sampling will be used, with two strata according to gestational age defined as follows: stratum 1 neonates <37 weeks and stratum 2 neonates ≥37 weeks. Blocked randomization (block of size 3) will be used for each stratum and for the allocation of participants to each of the intervention and control groups (1:1:1). The allocation sequence will be generated by Microsoft Excel®.

The random assignment will be concealed through the use of opaque envelopes, which will be sealed and numbered sequentially. These envelopes will be carried out by the operational coordinator of the project. The carbon paper inside the envelope will transfer the details of the random number and the group to which it will be assigned (A, B or C). This will ensure that the envelope is not permeable to intense light. The envelopes will be sealed with tamper-evident security tape and will be opened sequentially only after the participant, meeting the eligibility criteria, has received the envelope. The envelopes will be kept in a folder that will be kept on a locked shelf within each unit, which will be in the custody of the project's operational coordinator.

Blinding

It is not possible to blind the participants or the music therapist from randomization due to the nature of the intervention.

Variable Matrix

Variable name	Operational Definition	Nature and Scale of Measurement.	Unit of measurement
Date of birth	Time in which he was born.	Quantitative – Discrete	Day/Month/Year

Sex	Biological characteristics that determine whether it is female or male.	Qualitative – Nominal – Dichotomous	1: Female 2: Male

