A descriptive analysis of the variables will be performed using absolute and relative frequencies for the qualitative variables, as well as measures of central tendency and dispersion for the quantitative variables according to their normal distribution evaluated through the Kolmogorov-Smirnov test. To compare the data between the groups, one-way ANOVA or Kruskal-Wallis and chi-square ANOVA will be used. To determine the effect of music therapy on vital signs, repeated measures ANOVA or the Friedman test, if applicable, will be used. Assumptions of normality, homoscedasticity and residual distribution will be evaluated. Post-hoc comparisons are performed to determine significant differences between groups using the Student t-test. The level of significance for statistical tests will be $p < 0.05$.

A multivariate logistic regression will be performed to evaluate the effect of music therapy on respiratory rate, heart rate and pulse oximetry, considering confounding variables such as the number of visits, parental singing prior to the intervention, admission diagnosis, gestational age, comorbidities and gender.

Ethical Considerations

This research will adhere to the ethical guidelines developed by the CIOM and the WHO, as well as the stipulations of the Declaration of Helsinki for research involving human subjects. This will ensure the respect and protection of human rights, as well as the protection of the life, health, privacy, and dignity of the study subjects (24). Furthermore, this research is founded upon the tenets of bioethics, with the objective of promoting and ensuring justice, beneficence, non-maleficence, and patient autonomy, as outlined in the Belmont report from 1979 (25). Additionally, this research will have a social and scientific value, as its findings could potentially enhance the health of subjects and transform the manner in which care is delivered through the generation of reliable and valid results derived from a clinical trial. The researchers are highly qualified for the development of this research due to their expertise in pediatric and neonatal medicine, as well as epidemiology. For the administration of the interventions, a company with a high trajectory and experience in these interventions will be hired.

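### Allocation is stratified by gestational age, but the ANOVA-type, rank and t-tests omit the stratum, so level comparisons between infants are conservative if gestational age predicts the outcome

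*Protocol*

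**What the plan says.** Under Sample Selection the protocol stratifies the sample, "with two strata according to gestational age defined as follows: stratum 1 neonates <37 weeks and stratum 2 neonates ≥37 weeks", and allocates 1:1:1 in blocks of 3 within each stratum.

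Under Analysis of information it names the tests. The first sentence on comparisons is: "To compare the data between the groups, one-way ANOVA or Kruskal-Wallis and chi-square ANOVA will be used". The next is: "To determine the effect of music therapy on vital signs, repeated measures ANOVA or the Friedman test, if applicable, will be used". Post-hoc comparisons between groups are by Student t-test. None of these is described with a stratum or gestational-age term. A second paragraph plans a multivariate logistic regression for respiratory rate, heart rate and pulse oximetry, with gestational age among several listed confounders.

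Under Sample size the heart-rate means are 140 (live), 127 (pre-recorded) and 147 bpm (control), with 95% confidence and 90% power. The result is: "A total sample size of 45 was calculated, with a ratio of 1:1:1 between groups". No SD is given, and no gain from stratification is mentioned.

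**The concern.** Balancing the arms within each stratum takes the preterm-term difference out of the arm contrast. A test without the stratum still leaves that difference in its error term. The reported standard error is then larger than the true one, p-values are too large and confidence intervals too wide. The estimate itself is not biased.

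The protocol gives some reason to expect a stratum effect. Its Background ties stress to variability of heart and respiratory rate and says that such effects are stronger in preterm infants. If so, the trial goes to the trouble of stratifying and then discards the precision it could have gained, with only 15 infants per arm.

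**Working it through.** **Inputs from the protocol.** Three arms of 15 (N = 45), means 140, 127 and 147 bpm, significance level 0.05, power 90%, and two strata with blocks of 3.

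**Assumptions, because the protocol gives no figure.** The SD of heart rate is back-solved below. The share R² of heart-rate variance explained by the stratum is taken from 0 to 0.30. The strata hold 24 and 21 infants, with arms exactly balanced in each.

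**Step 1, the plan's own figure.** The grand mean is (140 + 127 + 147)/3 = 138, with deviations 2, −11 and 9. The SD of the means is √[(4 + 121 + 81)/3] = √68.67 = 8.287 bpm. A one-way ANOVA has noncentrality N·f², with f = 8.287/SD. Solving for 90% power at N = 45 (2 and 42 df) gives f = 0.550, so SD = 8.287/0.550 ≈ 15.07 bpm. With SD = 15, power is 90.3% and N is 45. So the stated size fits a plain unstratified ANOVA with an SD of about 15 bpm, but the document alone does not reproduce it.

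**Step 2, the standard error.** An unadjusted pairwise contrast reports SD_total × √(2/15). With balance within strata, its true standard error is SD_within × √(2/15), and SD_within = SD_total × √(1 − R²). If 15.07 is the total SD, the reported value is 15.07 × 0.365 = 5.50 bpm. At R² = 0.10 the true value is 5.50 × 0.949 = 5.22 bpm. At R² = 0.30 it is 5.50 × 0.837 = 4.60 bpm.

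**Step 3, type I error and power of the three-arm test on a level.** Simulation with 20,000 runs per scenario for type I error and reading (a), and 40,000 for reading (b). In (a), 15.07 is the total SD. In (b), it is the within-stratum SD. The preterm-term difference shown is the one used in (b).

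| R² | True/reported SE | Type I, no stratum | Type I, with stratum | (a) Power, no stratum | (a) Power, with stratum | (b) Difference, bpm | (b) Power, no stratum | (b) Power, with stratum |
|---|---|---|---|---|---|---|---|---|
| 0 | 1.000 | 5.0% | 4.9% | 90.2% | 90.2% | 0 | 89.8% | 89.7% |
| 0.05 | 0.975 | 4.2% | 5.0% | 90.0% | 90.9% | 6.9 | 88.6% | 89.8% |
| 0.10 | 0.949 | 3.4% | 4.8% | 90.8% | 93.0% | 10.1 | 87.4% | 90.1% |
| 0.20 | 0.894 | 2.4% | 5.2% | 91.2% | 95.1% | 15.1 | 83.4% | 90.0% |
| 0.30 | 0.837 | 1.4% | 5.1% | 92.3% | 97.6% | 19.8 | 77.2% | 89.8% |

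In (a), the gap between the two analyses runs from 90.9 − 90.0 = 0.9 to 97.6 − 92.3 = 5.3 points. The noncentral F with 41 error df puts adjusted power at 91.4% to 97.5% for R² from 0.05 to 0.30, about 1 to 7 points above the stated 90%. In (b), the gap runs from 89.8 − 88.6 = 1.2 to 89.8 − 77.2 = 12.6 points.

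**Step 4, a pairwise test.** Take live against pre-recorded (140 − 127 = 13 bpm), a within-stratum SD of 15.07 and a 15 bpm stratum difference. Power is 0.53 with the planned t-test and about 0.64 from the model with the stratum. With no stratum difference the two are 0.63 and 0.64, so pooling the error over three arms explains only about 0.01 of the gap.

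**Step 5, a within-infant test.** Two time points were simulated with an assumed between-infant SD of 11 and within-infant SD of 10 bpm, and the arm difference present only at the second. The unadjusted test of change had power 0.93 with no stratum offset and 0.93 with a 20 bpm offset. Type I error was 4.9% in both cases. A constant offset cancels from each infant's change. For the level at the second time point, the same 20 bpm offset cut unadjusted power from 0.91 to 0.78.

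**The case against.** Four objections carry weight.

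- A reader might infer that every comparison of the arms ignores gestational age. That is not so, because the planned regression lists it. The regression does not cure the omission, however. It is logistic while the three vital signs are defined as quantitative, and the protocol assigns the effect of music therapy to repeated measures ANOVA or Friedman.
- A reader might also infer that the stated 90% power is lost. The protocol does not support this. Its calculation fits an unstratified ANOVA, whose natural SD is the total SD, and on that reading unadjusted power stays at or above 90% for every R² tried. A shortfall appears only if the unstated SD is a within-stratum one.
- The test named for the effect is a repeated-measures one. Its arm-by-time term, like Friedman's ranking within each infant, removes a constant preterm-term offset. The quoted one-way ANOVA sentence follows the descriptive analysis and may be meant largely for group characteristics. This narrows the point to the arm main effect, comparisons at one time point and the t-tests. The protocol does not say which term is primary, so these remain in play.
- The error is in the safe direction, its size is unknown, and model terms are often left to a statistical analysis plan. All true. Still, the protocol has already named tests such as one-way ANOVA and the Student t-test, which by construction have no stratum term.

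**Conclusion.** The omission is real and worth correcting, but it costs precision and does not threaten validity. Where the planned tests compare levels between infants, they are conservative to the extent that gestational age predicts the outcome. Under assumed R² of 0.05 to 0.30, type I error is about 4.2% to 1.4%. The power forgone is about 1 to 5 points if the roughly 15 bpm planning SD is a total SD, and about 1 to 13 points if it is a within-stratum SD. At R² of 0.05 or less the loss is only about a point, and at zero there is none.

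The figures rest on the back-solved SD, the 24/21 split, exact balance within strata and normal errors. The power figures are for heart rate. The same mechanism applies to respiratory rate and saturation, but the protocol gives no planning values for them.

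**What to change.** Under Analysis of information, state that the between-arm and repeated-measures model for heart rate, respiratory rate and saturation includes the randomisation stratum (below 37 weeks, or 37 weeks and over) as a fixed factor. Take the three pairwise arm contrasts from that model in place of separate t-tests. If a between-arm rank test is needed, use a stratified one of the van Elteren type.

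The cost is a sentence or two of wording and one degree of freedom (42 to 41 for error). If the stratum explains nothing, calculated power moves from 90.0% to 89.9%. No new data are needed, since the stratum is known for every infant at randomisation.

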Heart rate	Number of heartbeats measured at minute 0, from minute 0 to 30 minutes after the procedure continuously and 30 minutes after the intervention.	Quantitative – Discrete	Beats per minute (bpm)
Respiratory rate	Number of breaths measured at minute 0, from minute 0 to 30 minutes after the intervention continuously and at 30 minutes after the intervention.	Quantitative – Discrete	Breaths Per Minute (rpm)
Oxygen saturation	Measurement of the percentage of oxygen availability in the blood, measured at minute 0, from minute 0 to 30 minutes after the intervention continuously and at 30 minutes after the intervention.	Quantitative – Discrete	Percentage of SaO ₂ (SaO ₂ %)

Description of interventions

Music therapy is a non-pharmacological therapeutic intervention that will be implemented through two modalities: live and pre-recorded music. Group A will be comprised of patients who have been exposed to live music, which will be carried out by a music therapist using the guitar as the only musical instrument. Instrumental lullabies will be used, which will be selected by the patients' legal guardians. Group B corresponds to patients who will be exposed to pre-recorded music, of the genre of lullabies, instrumental type, using a speaker that will be placed inside the patient's incubator. Group C will be those patients in whom no musical intervention will be performed.

The patient will be placed in an incubator, monitored with a vital sign monitor and pulse oximetry, and under the supervision of a research assistant. The research assistant will be responsible for recording the variables at minute 0, from minute 0 to minute 10, and 30 minutes after the completion of music therapy or non-intervention. The volume will be controlled in the three groups by means of a decibel regulator, with a maximum volume of 70 dB.

During the intervention and for a period of 30 minutes following its conclusion, singing will be prohibited by the music therapist or, in the case of groups A and B, by the parents. This prohibition will be implemented in the same manner in group C, which will be devoid of any form of music exposure in order to prevent the introduction of confounding variables. Both live and pre-recorded music will be instrumental in nature, lacking any lyrics. In accordance with the protocol for admission to the neonatal unit, the use of electronic devices is restricted. Consequently, patients will not be exposed to auditory stimuli of this nature.

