Sources of information

The source of information will be primary. Demographic and clinical data will be obtained from the medical record. The vital signs data such as heart rate, respiratory rate and oxygen saturation will be obtained from the records of the monitors of the intensive care units, at the established times, which are: at minute 0, from minute 0 to minute 10 continuously and at 30 minutes after the intervention.

Standardization of measurements

For the standardization of measurements of the different physiological variables, several elements will be considered. First, the trademark of the medical equipment manufacturer of each of the tools that will be used (vital sign monitor and pulse oximeter) will be verified, verifying that they correspond to the same commercial brand since they are different brands, there may be variability between the standard calibration measurements considered within the critical range. Second, it will be verified that each medical tool used has been calibrated in the last 6 months, recording the date of last calibration so that the device can be used during the study.

Subsequently, the professional in charge of the music company will verify that the guitar to be used during the live music is in tune and suitable for use. A decibel regulator will be used during the implementation of the pre-recorded and live music, which will adjust the volume of the sound emitted. to ensure the same decibels per research subject, with a maximum allowable of 70 dB. Vital variables will be recorded at minute 0, from minute 0 to minute 10 and at 30 minutes after the intervention.

Primary Outcome

The primary outcome of this study is the heart rate (HR), which will be measured through pulse oximetry every minute, beginning at minute 0 (prior to the intervention), then from minute 0 to minute 30 (during the intervention), and finally at 30 minutes after the intervention.

Secondary Outcomes

- Respiratory rate (RR) will be measured through pulse oximetry every minute, beginning at minute 0 (prior to the intervention), then from minute 0 to minute 30 (during the intervention), and finally at 30 minutes after the intervention.
- Oxygen saturation (SO) will be measured through pulse oximetry every minute, beginning at minute 0 (prior to the intervention), then from minute 0 to minute 30 (during the intervention), and finally at 30 minutes after the intervention.

Analysis of information

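### The Friedman test, named as the fallback for the effect of music therapy, ignores trial arm and so tests change over time pooled across arms

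*Protocol*

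**What the plan says.** All the relevant analysis text is in the protocol's Analysis of information section.

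- The sentence that sets the test of the treatment effect reads: "To determine the effect of music therapy on vital signs, repeated measures ANOVA or the Friedman test, if applicable, will be used".
- The sentence before it reads: "To compare the data between the groups, one-way ANOVA or Kruskal-Wallis and chi-square ANOVA will be used". It names no outcome, time point or change score.
- A later sentence reads: "Post-hoc comparisons are performed to determine significant differences between groups using the Student t-test".
- The next paragraph adds a logistic regression for the effect of music on respiratory rate, heart rate and oximetry, "considering confounding variables such as the number of visits, parental singing prior to the intervention, admission diagnosis, gestational age, comorbidities and gender".

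The design is set elsewhere. Under Sample size: "A total sample size of 45 was calculated, with a ratio of 1:1:1 between groups". Under Description of interventions, live music and pre-recorded music go to two separate groups of infants, and "Group C will be those patients in whom no musical intervention will be performed". Under Primary Outcome, heart rate is read every minute, "beginning at minute 0 (prior to the intervention), then from minute 0 to minute 30 (during the intervention"), and once more 30 minutes afterwards. Description of interventions, Sources of information and Standardization of measurements instead give a recording window of minutes 0 to 10.

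**The concern.** The effect of music in this trial is a difference between groups of different infants. Friedman is a one-factor, within-subject rank test: it asks whether readings at some times tend to rank above readings at others within the same infant. Nothing in it represents arm or arm-by-time.

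Repeated measures ANOVA can carry arm as a between-infant factor, so the two methods joined by the word *or* do not answer the same question. Moving from the first to the second because assumptions fail would change the hypothesis, not just the method.

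An infant who settles during a quiet, supervised observation period may show a falling heart rate in every arm, control included. On the Friedman branch that shared fall could be written up as an effect of music therapy.

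**Working it through.** **1. The statistic does not use arm.** With n = 45 infants and T readings each, let R_j be the sum over all infants of the within-infant rank of reading j. Then

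χ²_F = 12 / [nT(T+1)] × Σ R_j² − 3n(T+1).

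Arm appears nowhere in this. In a simulated data set, p was 0.000257 both before and after the infants were shuffled across arms. This step rests on no assumed number. Running Friedman separately in each arm does not help: with a 10 bpm fall common to all arms (three readings, SD 15, correlation 0.5), it rejects in 57% of runs within a single arm of 15.

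**2. A plausible SD.** The protocol gives means of 140, 127 and 147 bpm, 90% power and N = 45, but no SD, so 45 cannot be reproduced from its own inputs. Working backwards:

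- Grand mean = (140 + 127 + 147)/3 = 138.
- SD of the means = √[(2² + 11² + 9²)/3] = √(206/3) = 8.29.
- Noncentral F with 3 groups and α = 0.05 gives 90% power at N = 45 when SD = 15.07 (f = 8.29/15.07 = 0.55), and at N = 42 when SD = 14.52.

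SD 15 is therefore used below, as an assumption.

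**3. Number of readings.** Minute 0, minutes 1–10 and one later reading make 1 + 10 + 1 = 12. Minute 0, minutes 1–30 and one later reading make 1 + 30 + 1 = 32. Both are shown because the sections differ.

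**4. No arm effect, common 8 bpm fall in all arms** (15 per arm, SD 15, 2,000 replicates; rejection rate of Friedman at 0.05):

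| Readings | Correlation | Step fall after minute 0 | Linear fall |
|---|---|---|---|
| 12 | AR(1), 0 to 0.8 | about 50–75% | about 60–70% |
| 32 | AR(1), 0 to 0.8 | about 34–42% | about 70–95% |
| 32 | equal, 0.5 | 71% | higher still |

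Kruskal-Wallis across arms on change from minute 0 stays at about 4–5% throughout. Part of the AR(1) excess is a separate distortion: with 32 readings, AR(1) 0.8 and no fall at all, Friedman already rejects in about 12–15%.

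**5. The planned effect.** Take the planning means as falls from a common 147: live −7, pre-recorded −20, control 0 (three readings, SD 15, correlation 0.5). Friedman rejects in about 86% and Kruskal-Wallis on change in about 96%. Over SD 12–20 the ranges are roughly 65–95% and 77–99.7%. Friedman's rejections here come from the pooled downward trend, not from a contrast of arms.

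**6. Opposite effects.** With −10, +10 and 0 bpm, the pooled trend cancels. Friedman then rejects in about 3% and Kruskal-Wallis on change in about 95%.

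**The case against.** The strongest reply is that the section already holds between-arm analyses. Kruskal-Wallis is named one sentence earlier for comparing groups, the post-hoc t-tests are explicitly between groups, and the logistic regression is aimed at the music effect on heart rate itself. On a generous reading, Kruskal-Wallis is meant for arms and Friedman for time within infants. Friedman is also conditional, marked as used if applicable.

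Much of this stands. A reader might infer that the plan has no valid comparison of arms, and that would be wrong. Repeated measures ANOVA with arm as a factor is sound and is not criticised. But the generous reading is not what the sentence says: it gives Friedman the task of determining the music effect. Kruskal-Wallis is not tied to heart rate, a time point or a change. The t-tests would follow an omnibus test that had not compared arms. The logistic regression needs a categorical outcome that the section does not define, and it is not offered as a substitute.

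A reader might also infer that Friedman would miss the effect the trial is planned to find. The documents do not support that. Both music arms are planned below control, and in that case Friedman usually rejects, though for the wrong reason. The 3% figure needs effects in opposite directions, which is not the planned scenario.

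Friedman could compare arms if each randomisation block of three were the unit of ranking. The protocol does not say so, and pairing it with repeated measures ANOVA points to time.

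**Conclusion.** The point holds as a fault in one stated fallback and should be fixed. That Friedman over time cannot test a difference between arms is a property of the test and is certain. How often it would mislead is not certain: the rates depend on an assumed SD, correlation, shape of the shared change and number of readings. On the protocol's own schedules they are well above 5% in every falling scenario examined, from about a third of trials upwards.

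Exposure is conditional. Heart rate, the primary outcome, is affected only if the assumptions for repeated measures ANOVA are judged to fail. Oxygen saturation, a percentage that cannot exceed 100, is the likelier case.

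**What to change.** In Analysis of information, delete Friedman as the test of the music-therapy effect. Make the fallback a between-arm test of the same contrast as the main analysis. The Kruskal-Wallis test already named would serve, as would rank ANCOVA, applied to change from minute 0. State this for heart rate and likewise for respiratory rate and oxygen saturation. If a description of change over time is wanted, Friedman may stay for that purpose, labelled as within-infant and not as evidence of a music effect. The cost is a change of wording; all the data are already collected.

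Optional and separate: adjust the between-arm comparison for the minute-0 value and the gestational-age stratum. This gains precision and corrects no bias. In simulation with SD 15 and a single later reading, three-arm power at N = 45 rises from 90% to about 92%, 96% and 99.6% at assumed correlations of 0.3, 0.5 and 0.7, for two degrees of freedom.

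### Two unranked analyses, one without named covariates and one adjusted for confounders, address the effect on heart rate, and the protocol does not say which decides the primary outcome

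*Protocol*

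**What the plan says.** The Primary Outcome section names heart rate, with readings at minute 0, during the intervention and 30 minutes after it. Analysis of information then assigns the treatment effect on it twice.

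- First analysis: "To determine the effect of music therapy on vital signs, repeated measures ANOVA or the Friedman test, if applicable, will be used". No covariates are named.
- Second analysis, in its own paragraph: "A multivariate logistic regression will be performed to evaluate the effect of music therapy on respiratory rate, heart rate and pulse oximetry". This one is adjusted for six named confounders, among them parental singing, gestational age and comorbidities. They are introduced by way of example, so the list is open.

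On the threshold, the section has one sentence, beginning "The level of significance for statistical tests will be"; the value it sets is 0.05. This sentence closes the paragraph before the regression but is worded for tests in general, and no other level appears. The section labels neither analysis as primary, supportive or sensitivity. It gives no order of testing and no rule for what is concluded if the two disagree.

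**The concern.** Both analyses are asked the same question about the same primary outcome. An adjusted analysis beside an unadjusted one is ordinary practice when one of them is designated in advance. Without that, a trial of 45 infants could obtain p < 0.05 from one and not the other, and the text would not settle which is the trial's answer. If either were accepted, the claim on heart rate would have two chances at the full 5% level, and its error rate would exceed the stated one.

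This is separate from which time point counts and from whether logistic regression suits heart rate. Settling both of those would still leave two unranked analyses.

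**Working it through.** **Inputs from the protocol.** Three arms of 15, total 45; alpha 0.05; power 90%; mean heart rates 140 (live), 127 (pre-recorded) and 147 bpm (control), all from Sample size. Six covariates are named in Analysis of information.

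**Assumptions, not in the protocol.** One heart-rate value per infant; a linear adjusted model with six covariates; covariate R² from 0 to 0.6.

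**Step 1: does the sample size identify the deciding test?** The section names no test and gives no SD.
- Grand mean = (140 + 127 + 147)/3 = 138.
- Spread of means = √[(2² + 11² + 9²)/3] = √(206/3) = 8.287 bpm.
- Effect size f = 8.287/SD. For a one-way ANOVA at 90% power, SD 12 gives N = 30, SD 15 (f = 0.552) gives N = 45 with power 0.903, and SD 20 gives N = 78.
- N = 45 results exactly when the SD is about 14.5 to 15.1 bpm.

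So 45 is compatible with an ANOVA of group means and is not shown to be wrong. It cannot be reproduced from the stated inputs alone, and it does not designate an analysis.

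**Step 2: reference values.** For two two-sided 0.05 tests with correlated normal statistics, P(at least one rejects) = 1 − P(|Z₁| < 1.96 and |Z₂| < 1.96).
- Independent: 1 − 0.95² = 0.0975.
- Correlation 0.5: 0.0907; 0.8: 0.0781; 0.9: 0.0704; 0.95: 0.0646.

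**Step 3: simulation with no treatment effect.** There were 20,000 trials per setting, 3 × 15 infants. The test without covariates is a one-way F test. The adjusted test is the 2-df F test for arm in a linear model with six covariates. Disagreement is 2 × P(either) − P(first) − P(second).

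| Assumed R² | First alone | Adjusted alone | Either | Disagreement |
|---|---|---|---|---|
| 0 | 0.0494 | 0.0487 | 0.0667 | 0.035 |
| 0.2 | 0.0488 | 0.0473 | 0.0747 | 0.053 |
| 0.4 | 0.0508 | 0.0520 | 0.0847 | 0.067 |
| 0.6 | 0.0467 | 0.0521 | 0.0879 | 0.077 |

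Each test alone holds about 5%, so the excess comes only from having two of them. Separate runs of the same design at R² of 0 to 0.5 gave 0.066 to 0.087 for either test, with disagreement in 3% to 7% of trials.

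**The case against.** The strongest reply is that this is an omission of a kind often left to the statistical analysis plan, and that the protocol already points to an order. The primary objective uses the same verb, to determine, as the ANOVA sentence. The sample size rests on three group means, which suits an ANOVA and not a logistic model. The regression comes last, with confounding as its stated role. These cues are real and make the ANOVA the likelier intention. They are still hints. The protocol does not defer the choice; it fixes two analyses for its own primary outcome and ranks neither.

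Several limits also stand:
- That the 0.05 level covers the regression is an inference from general wording.
- The simulation stands in for both planned analyses. It uses one value per infant in place of repeated measures, and a linear model in place of a logistic one.
- The Friedman test compares times within infants, not arms, so that option does not address the between-arm effect in the same way.
- Heart rate is in bpm with no cut-off defined, so the logistic regression cannot be run on it as written.

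A reader might infer three stronger things, none of which the documents support:
- That the protocol permits success to be claimed on either analysis. It is silent; it does not say so.
- That the two results will usually conflict. Under no effect they disagree in well under one trial in ten.
- That the inflation is much larger because the regression is logistic. That requires a split of heart rate which the protocol does not specify. It also mixes in a different problem: with a split at the median, the likelihood-ratio test alone rejected in about 8.9% of simulated null trials, whether or not a second analysis existed.

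**Conclusion.** The point holds as a modest defect in a place that matters. Two analyses of the primary outcome are planned, neither is designated, and the available cues do not amount to a designation. If either could carry the claim, the false-positive rate would be about 0.065 to 0.09, an excess of roughly 1.5 to 4 percentage points over 0.05. The excess is present even when the covariates explain nothing (0.067). Disagreement would be roughly 3% to 7% of null trials for R² up to 0.5, and just under 8% at 0.6.

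These sizes are conditional on the assumptions listed with the calculation, above all the R², for which the protocol gives no figure. If the sponsor always meant the ANOVA alone to decide, there is no inflation from this source, and a sentence saying so would remove the ambiguity.

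**What to change.** In Analysis of information, name one analysis that decides the heart-rate outcome. Labelling one of the two existing analyses would remove the ambiguity. A better choice is a linear model of one pre-specified heart-rate summary on arm, adjusted for minute-0 heart rate and gestational-age stratum, at two-sided 0.05. It uses a baseline reading already collected and respects the stratification already used in the randomisation.

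State that the confounder-adjusted regression is a sensitivity analysis, run as a linear model because heart rate is in bpm with no cut-off. It should be reported as estimates with 95% confidence intervals, and it cannot establish or overturn the primary conclusion. The same order can be applied to respiratory rate and oxygen saturation.

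The cost is a few sentences, with no extra patients or data. There are two real consequences. The heart-rate summary must be fixed in advance, including its recording window, which runs to minute 10 in some sections and minute 30 in others and needs reconciling. And a result significant only in the sensitivity analysis can no longer be claimed as the trial's finding.
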